### 5.2.2 On-demand treatment

Patients in arm 1 will continue on-demand treatment with their usual bypassing product until visit 9 (end of main part for arm 1). Patients included prior to the treatment pause will re-start the trial at visit 9a; see Section [5.1](#). Novo Nordisk will not provide or reimburse on-demand treatment for patients in arm 1. In the extension part, patients in arm 1 will receive daily concizumab subcutaneous injections (see Section [5.2.1](#)).

### 5.2.3 Treatment of break-through bleeding episodes

The patient must contact the site when they have a suspected bleed, see Section [9.2.3](#) for further details.

Novo Nordisk will not provide or reimburse bypassing treatment for bleeding episodes. Any bleeds occurring in the trial can be treated with the patient's usual factor-containing product taking the treatment guidance in [Appendix 11](#) into consideration. [Table 3](#) provides a tabular overview of the guidance on management of mild and moderate bleeds. Prophylactic treatment with concizumab should continue independent of bleeding episodes and their treatment, i.e. the original dosing schedule should be maintained unless investigator judges otherwise.

For treatment of bleeds with aPCC (FEIBA®), the dose must not exceed a single dose of 50 U/kg, and not exceed 100 U/kg within 24 hours. The first treatment should be at the hospital, with observation of the patient for a minimum of 24 hours. If there are no safety concerns, the patient can continue with FEIBA® treatment for breakthrough bleeds at home. Single dose home treatment must not exceed 50 U/kg. If an additional dose is needed because a single dose was insufficient to treat the bleed, the patient must come to the site.

For treatment of bleeds with ByClot®, the dose must not exceed 60 µg/kg, and not exceed 90 µg/kg within 24 hours. Additional dose can be given at an interval of 8 hours or longer. The first treatment should be at the hospital, with observation of the patient for a minimum of 24 hours. If there are no safety concerns, the patient can continue with ByClot® treatment for breakthrough bleeds at home. Single dose home treatment must not exceed 60 µg/kg. If an additional dose is needed because a single dose was insufficient to treat the bleed, the patient must come to the site.

**Table 3 Guidance on management of mild and moderate bleeds during concizumab PPX**

|                               | rFVIIa                                                                                                                                                                   | aPCC                                                                         | ByClot ®                                                                                                    |
|-------------------------------|--------------------------------------------------------------------------------------------------------------------------------------------------------------------------|------------------------------------------------------------------------------|------------------------------------------------------------------------------------------------------------------------|
| Contact centre (PI)    | The patient must contact the centre before initiating treatment of a bleeding episode. If more doses are needed, the patient should contact the centre before each dose. |                                                                              |                                                                                                                        |
| First dosea | 90 µg/kg                                                                                                                                                                 | Single dose must not exceed 50 U/kg, and not exceed 100 U/kg within 24 hours | Single dose must not exceed 60 µg/kg ByClot ® , and not exceed 90 µg/kg ByClot ® within 24 hours |
| Second dose            | 90 µg/kg                                                                                                                                                                 | At investigator's discretion                                                 | Additional dose can be given at an interval of 8 hours or longer                                                       |
| Dose interval          | Time between first and second dose must not be shorter than stated in local labelling b                                                                       |                                                                              |                                                                                                                        |
| Anti-fibrinolitics     | Local/topical use is allowed. Use of single systemic doses is allowed after careful benefit-risk evaluation                                                              | Not recommended                                                              | Not recommended                                                                                                        |

**Notes:** aLowest dose in accordance with local labelling. bThe interval between the two doses could be increased based on clinical case-by-case judgment keeping in mind that early breakthrough bleed control remains crucial.

### ***Severe and life-threatening bleeding episodes***

From a patient safety perspective, specific recommendations for the management of severe and life-threatening bleeding episodes (see definition in [Table 10](#)) are not considered feasible as such management often poses several complex clinical challenges that need to be addressed case by case by the treating physicians hereby tailoring and securing the optimal treatment, which in some cases may be high factor replacement doses for extended periods of time. In the rare event of a severe

(life-threatening) bleed the patient should be in immediate and close contact to the investigator and be treated with relevant doses of factor containing products at the discretion of the investigator.

Please see Section [9.2.3](#) and [Appendix 11](#) for further instructions on bleeding episodes.

#### **5.2.4 Treatment during screening and follow-up period**

Patients should follow their normal prophylaxis schedule or on-demand regimen during the screening period and follow-up period. Treatments will not be reimbursed by Novo Nordisk. Bleeds during screening and follow-up should be treated as per standard local practice.

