## 5 Trial design

### 5.1 Overall design

This is a prospective, multicentre, open label clinical trial with four arms. The trial aims to evaluate the effect and safety of daily concizumab prophylaxis administered s.c. in patients with HAWI and HBWI. Initially, patients were randomised to concizumab PPX or no PPX or assigned into the non-randomised treatment arms, based on their treatment regimen before entering the trial. After the restart of the trial, the patients will enter the treatment arm they were initially assigned to. New patients eligible for arms 1 and 2 will be randomised to concizumab PPX or no PPX. The main part of the trial is completed for a patient when the patient has completed at least 24 weeks of participation (screening period not included) for patients in arm 1 or 32 weeks of participation (screening period not included) for patients in arms 2,3 and 4. After the main part of the trial, all patients will be offered to continue in the extension part of the trial and receive treatment with concizumab for up to an additional 128 weeks (arms 2–4) or 136 weeks (arm 1); [Figure 1](#).

A *primary analysis cut-off* is defined as when all patients in arm 1 have completed visit 9/9a (or withdrawn) and all patients in arm 2 have completed visit 10a (or withdrawn). Furthermore, a 56-week cut-off is defined as when all patients in arms 2, 3 and 4 have completed visit 13a (or permanently discontinued treatment). At this 56-week cut-off, an additional evaluation will be made assessing bleed related endpoints and safety.

[figure not shown]
After the last patient has been randomised, any patient that due to the COVID-19 pandemic is prevented from restarting the new dosing regimen will no longer be used to determine the primary analysis cut-off and the 56-week cut-off.

After up to 128/136 weeks in extension part the patient will enter the safety follow-up part of the trial. The patient will receive his last dose at home on the day prior to visit 26a. The follow-up part of the trial lasts for 7 weeks and the patient will continue to report bleeding episodes until visit 27a.

In this version of the protocol, patients not already enrolled at the time of the re-start, will be defined as new patients recruited from the non-interventional study NN7415-4322 (explorer 6) and from outside the concizumab programme. New patients can belong to the following categories:

- patients who were in screening phase at the time of the pause

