## 4 Analysis sets

For the purposes of analysis, the following analysis sets are defined for the week 56 cut-off.

Subject Analysis Set	Description
Full Analysis Set (FAS)	All subjects randomised to concizumab PPX or on-demand treatment or allocated to arms 3 or 4. Subjects from arms 1 and 2 will contribute to the evaluation ‘as randomised’.
Safety Analysis Set (SAS)	All subjects exposed to concizumab PPX or randomised to on-demand treatment. All subjects will contribute to the evaluation ‘as treated’.

Defined Analysis Data Sets	Description
On-treatment	
The time period where subjects are considered to be affected by on-demand treatment or concizumab treatment.
 
For safety endpoints/assessments relating to events (number of thromboembolic events, number of hypersensitivity type reactions, number of injection site reactions, number of patients with antibodies to concizumab, number of adverse events) the ‘on-treatment’ analysis data set is defined as follows.
 
For subjects in arm 1 during on-demand treatment, the period begins on the date of randomisation (as registered in IWRS) and ends at the first occurrence of:
 

1. Time of permanently ending on-demand administration and initiation of any PPX regimen

2. The last direct subject-site contact, at or prior to the 56 weeks cut-off

3. Withdrawal date for subjects who withdraw informed consent

4. The last subject-investigator/site contact as defined by investigator for subjects who are completely lost to follow up

5. Date of death for subjects

 
For subjects in arm 1 during concizumab PPX treatment, the period begins at the time of initiation of concizumab PPX treatment and ends at the first occurrence of:
 

6. Date of last dose of concizumab + 7 weeks

7. Items 2., 3., 4. or 5. above

 
For subjects in arms 2-4 that start on the new concizumab dosing regimen and who have not been exposed to the initial dosing regimen, the period begins at the time of start of the new concizumab PPX regimen.

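### Section 5.2.4 applies local practice to bleeds in follow-up, which starts about one day after the last concizumab dose, and leaves unclear whether the aPCC/ByClot limits still hold

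*Protocol*

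**What the plan says.** **Follow-up rule.** Protocol section 5.2.4 covers screening and follow-up together: "Bleeds during screening and follow-up should be treated as per standard local practice". On the background regimen it says: "Patients should follow their normal prophylaxis schedule or on-demand regimen during the screening period and follow-up period". It gives no dose limit and does not refer to section 5.2.3 or Appendix 11.

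**Timing.** Section 5.1: "The patient will receive his last dose at home on the day prior to visit 26a". Follow-up then lasts 7 weeks, to visit 27a.

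**Bleed-treatment rule.** Section 5.2.3 begins broadly: "Any bleeds occurring in the trial can be treated with the" patient's usual product, with Appendix 11 to be considered. For aPCC, "the dose must not exceed a single dose of 50 U/kg, and not exceed 100 U/kg within 24 hours". For ByClot the limits are 60 µg/kg for a single dose and 90 µg/kg in 24 hours. For both products: "The first treatment should be at the hospital, with observation of the patient for a minimum of 24 hours". Appendix 11 repeats these limits. Section 9.2.3 requires the investigator to instruct patients to contact the site before treating a breakthrough bleed.

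**Scope signals in the other direction.** The titles of Tables 3 and 22, and the summary of changes to reduce risk in section 3.3, describe the guidance as applying during concizumab prophylaxis.

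**Safety attribution.** For safety events, SAP section 4 defines the on-treatment set as "The time period where subjects are considered to be affected by on-demand treatment or concizumab treatment", and one of its end points is "Date of last dose of concizumab + 7 weeks".

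**The concern.** Screening and follow-up are different clinical states, yet they share one instruction. A new patient in screening has not received concizumab. A patient entering follow-up took a dose the day before.

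The bleed-treatment guidance exists because of thromboembolic risk. Section 3.3 reports that all 3 patients with thromboembolic events had used breakthrough bleed treatment just before symptoms began. In 2 of them a relatively high dose or prolonged factor treatment was reported, and those 2 had among the highest concizumab exposures. Section 5.6 says that concizumab exposure combined with other risk factors could contribute to thrombosis.

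At stake is whether a patient who still has appreciable concizumab exposure is treated for a mild or moderate bleed within the aPCC/ByClot limits and after contacting the site, or by whatever the local habit is. Section 4.3.2.2 counts thromboembolic events to week 167, so an event in follow-up would be reported within that endpoint. This is a patient-safety question and not one of inference.

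**Working it through.** No power or error-rate calculation applies. The check is a timeline and a side-by-side reading.

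**Timeline at nominal visit times** (flowchart in section 2; section 5.1; SAP section 4)
- Visit 26a: week 160, 160 × 7 = day 1120.
- Last dose, the day before: 1120 − 1 = day 1119.
- Visit 27a: week 167, 167 × 7 = day 1169.
- Length of follow-up: 1169 − 1120 = 49 days = 7 weeks. This reproduces the protocol's own figure.
- Gap from last dose to start of follow-up: 1120 − 1119 = 1 day. Dosing is daily, so this is one dosing interval, and exposure at the start of follow-up is about the pre-dose trough on treatment.
- SAP on-treatment limit: 1119 + 49 = day 1168, one day before visit 27a.

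The SAP supplied is for the 56-week cut-off. Its window is used here only as the sponsor's own rule for attributing safety events to concizumab. It is not a concentration measurement. Visit windows, and the global end date of 20 June 2024 in section 5.3, can change the actual length of follow-up for a patient.

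**Side-by-side reading for a mild bleed shortly after visit 26a**

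| Place | Instruction | Stated end |
|---|---|---|
| 5.2.3 text | aPCC 50 U/kg single dose, 100 U/kg in 24 h; ByClot 60 and 90 µg/kg; first treatment observed in hospital; site contact | None |
| 9.2.3 | Site contact before treatment; consider Appendix 11 | None |
| Appendix 11 text | Same caps, observation and contact | None |
| Titles of Tables 3 and 22; 3.3 | Same guidance | Tied to concizumab prophylaxis |
| 5.2.4 | Local practice | Covers follow-up by name |
| 7.7 | Move to a marketed product, at the investigator's discretion | No mention of Appendix 11 |

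**Two readings follow, and they are alternatives.**
1. *The guidance ends with prophylaxis, and 5.2.4 is the specific rule.* Its heading names the follow-up period, and the table titles support this scope. The caps, the first-treatment observation and the site contact then stop at visit 26a, about one day after the last dose. The sections do not conflict, but a gap opens at about trough exposure.
2. *Section 5.2.3 covers every bleed in the trial, and follow-up is part of the trial.* The caps then remain, but 5.2.4 gives a different instruction for the same bleed, and no text says which one prevails.

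Either way, a site cannot tell from the protocol which rule governs.

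**The case against.** The strongest reply is that the caps never lapse. Section 5.2.3 reaches all bleeds in the trial and words the aPCC/ByClot limits as mandatory, whereas 5.2.4 is worded as advice. Section 9.2.3 and the Appendix 11 text have no stop at visit 26a either. This stands in part: the lapse is one plausible reading and not the plain meaning. A reader might infer that 5.2.4 removes the limits outright, but the documents do not support that.

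A second reply is that the sponsor may have chosen this scope, within changes accepted by the external data monitoring committee (section 3.2), and that the reported risk lies elsewhere. Section 3.3 places all the reported events within 3 months of starting treatment, while nominal follow-up starts at week 160. No event after stopping is described, and exposure falls once dosing ends. During the pause, arm 2 patients stopped concizumab and received standard care (section 5.1), with no resulting harm described. All of this stands as context. It is absence of reported evidence and does not show that the first days after the last dose are free of risk.

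A third reply is that no departure from the caps is shown. That also stands. The documents do not say that local practice exceeds the limits, how many aPCC or ByClot users reach follow-up, or that the 3 patients with events received either product.

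Other safeguards continue: bleeds are recorded to visit 27a, the eDiary prompts patients to contact the investigator, and a single significant thromboembolic event triggers urgent review (section 9.3.9). None of these sets a dose limit.

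**Conclusion.** The point holds as an ambiguity in a safety instruction. On one reading the aPCC/ByClot caps, first-treatment observation and site contact end about one day after the last dose. On the other they continue, but 5.2.4 contradicts them without a stated order of precedence. Correcting it is a cheap improvement. It does not undermine the trial, and no analysis is affected.

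The size is a matter of scope only. The exposure argument is secure at the start of follow-up, because one day is one dosing interval. It rests on nominal visit timing and uninterrupted daily dosing up to the last dose. The documents give neither a half-life nor concizumab levels after the last dose, so no excess risk or patient count is claimed.

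Two stronger inferences should be resisted. First, because the SAP window nearly coincides with follow-up, a reader might conclude that relevant exposure lasts throughout. The window attributes events to treatment and says nothing about concentration. Second, since 5.2.4 returns patients to their normal regimen, and section 5.2.1 requires a 48-hour aPCC/ByClot wash-out before concizumab for patients coming from prophylaxis, a reader might conclude that a matching interval is needed afterwards. The documents do not establish that. Delaying prophylaxis could leave patients unprotected as concizumab wanes, so the timing is for the sponsor's clinical judgement.

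**What to change.** Split section 5.2.4:

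- **Screening:** keep local practice for patients not on concizumab.
- **Follow-up:** state that mild and moderate bleeds are treated taking section 5.2.3 and Appendix 11 into consideration, including the aPCC/ByClot caps, observation of a first treatment and site contact before treatment. Apply this for a stated period after the last dose, at most 7 weeks to match the SAP on-treatment window, and shorter if the sponsor's PK data support it.
- **Severe bleeds:** leave to the investigator's discretion, as section 5.2.3 already does.
- **Cross-reference:** point to this rule from section 7.7, so that it is seen when a patient stops concizumab and moves to a marketed product.

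Leave the timing of resumed aPCC/ByClot prophylaxis to the sponsor.

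The cost is a short wording amendment with no new data collection. The downside is slightly more restricted bleed treatment as concizumab wanes. A PK-based period and discretion for severe bleeds keep that small.

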### **5.3 Patient and trial completion**

Approximately 155 patients will be screened to achieve that at least 51 patients are randomly assigned to either no prophylaxis or trial product in the treatment arms 1 and 2. To achieve that up to 85 patients are assigned to prophylaxis with concizumab in treatment arms 3 and 4; please see [Table 2](#). For definition of screen failures; see Section [6.3](#).

#### **Trial period completion for a patient:**

Trial period completion for a patient is defined as when the patient has completed visit 27a, or at the global end of trial date 20 June 2024 whichever comes first.

#### **Treatment period completion for a patient:**

Treatment period completion for a patient is defined as when the patient has completed visit 26a.

### **5.4 End of trial definition**

The end of trial is defined as the date of the last visit of the last patient in the trial or 20 June 2024 whichever comes first.

### **5.5 Scientific rationale for trial design**

The trial design follows to the extent possible requirements and makes use of applicable elements outlined in the EMA guidelines on the clinical investigation of recombinant and human plasma-derived factor VIII/IX products in terms of; endpoints, patient population, sample size, eligibility criteria, exposure time, PK and immunogenicity assessment etc.

The primary objective of the trial is to compare concizumab prophylaxis (arm 2) compared to no prophylaxis (arm 1, on-demand treatment) in preventing bleeding episodes in HAwI and HBwI patients. Superiority to on-demand has been chosen as regulatory authorities have traditionally required a comparison of prophylaxis versus no prophylaxis for registration of haemophilia products for prophylaxis. The superiority analysis aims to demonstrate the effect of concizumab for HAwI and HBwI patients combined. The PD/PK effect of concizumab is expected to be comparable across haemophilia types. A separate superiority analysis for HBwI alone is not considered feasible, given the rarity of the disease. The combined analysis is also justified given the similarity of the diseases, the concizumab mode of action, and the comparability of the data from HAwI and HBwI in phase 2.

Patients to be included in the on-demand arm of the trial will be coming from on-demand treatment regimens at their clinics reflecting local standards of care. After completion of the main part of the trial, all patients will be offered concizumab prophylaxis in the extension part for up to an additional 136 weeks.

Due to the treatment pause (described in Section [3.2](#)), and subsequent restart of the trial, the original randomisation cannot be maintained after the treatment pause. The impact of potential resulting bias will be assessed with sensitivity analyses.

## 5.6 Justification for dose

Upon restart, the dosing regimen for this phase 3 trial is a loading dose of 1.0 mg/kg concizumab s.c. on the first day of treatment, followed by an initial daily dose of 0.20 mg/kg concizumab. Within the initial 5–8-week dose adjustment period on 0.20 mg/kg concizumab, the patients can be increased or decreased in dose to 0.25 mg/kg or 0.15 mg/kg concizumab (or they can stay on 0.20 mg/kg); this will be based on the concizumab exposure level at visit 4a/9a.2 (see Section [9.2.2](#)).

The reduction in the initial daily dose as compared to the previous maintenance dose of 0.25 mg/kg, is based on the finding that 2 of the 3 patients experiencing thromboembolic events were among the patients with the highest concizumab exposure level observed. Furthermore, the concizumab exposure levels observed in phase 3 on the original dosing regimen (0.25 mg/kg/day) were higher than expected based on the phase 2 results as well as population PK modelling. The safety of the initial daily dose of 0.20 mg/kg is supported by results from the phase 2 trials, since the exposure range observed in phase 2 covers the exposure range predicted when restarting all patients on daily dosing with 0.20 mg/kg concizumab. The exposure ratio between the initial daily dose of 0.20 mg/kg and the exposure level at the no adverse effect level (NOAEL) in the nonclinical studies is given in the Investigator's Brochure.

Some patients will need to increase or decrease the daily dose to 0.25 or 0.15 mg/kg; this will be based on the exposure level after 4 weeks of concizumab PPX (see Section [9.2.2](#)). The target of concizumab exposure levels above 200 ng/mL emanates from an exploratory exposure-response analysis performed based on the phase 2 trials (NN7415-4255 (explorer 5) and NN7415-4310 (explorer 4) main part data, indicating a lower ABR with exposure levels above 200 ng/mL. The upper limit of 4000 ng/mL is a precaution to avoid patients reaching very high exposure levels. Despite the lack of data showing that high exposure per se is causative of thromboembolic events, the evaluations of the thromboembolic events suggests that the concizumab exposure in combination with other risk factors could contribute to thrombosis.

